3.1 Inclusion Criteria

1. Signed Written Informed Consent

- Subjects must have signed and dated an IRB/IEC approved written informed consent form in accordance with regulatory and institutional guidelines. This must be obtained before the performance of any protocol related procedures that are not part of normal subject care
- Subjects must be willing and able to comply with scheduled visits, treatment schedule, laboratory tests, tumor biopsies, and other requirements of the study.

2. Signed Written Informed Consent

- All subjects must be either recurrent, unresectable or Stage IV AJCC (7th edition) and have histologically confirmed Merkel cell carcinoma with confirmed pathology in order to be eligible. Please refer to Appendix 1 or description of AJCC 7th editions of TNM and staging.
- At least 18 years of age
- ECOG PS < 2
- Active disease measurable by CT, MRI, or clinical exam
- Prior chemotherapy or immunotherapy will be allowed if new or persistent measurable site(s) of disease are present.
- Prior radiation therapy will be allowed if there is active measurable disease burden.
- All subjects must have at least 2 distinct lesions as documented by a complete physical examination or imaging studies within 4 weeks prior to randomization. Imaging studies must include a CT scan of the involved disease sites and all known sites of resected disease and brain magnetic resonance (MRI) or CT (brain CT allowable if MRI is contraindicated or if there is no known history of resected brain lesions).
- Tumor tissue from the core biopsy or resected site of disease must be provided for biomarker analyses. Prior surgery that required general anesthesia must be completed at least 4 weeks before study drug administration. Surgery requiring local/epidural anesthesia must be completed at least 72 hours before study drug administration.
- All baseline laboratory requirements will be assessed and should be obtained within 14 days of randomization. Screening laboratory values must meet the following criteria.

- i) WBCs $\geq 2000/\mu\text{L}$
- ii) Neutrophils $\geq 1500/\mu\text{L}$
- iii) Platelets $\geq 100 \times 10^3/\mu\text{L}$
- iv) Hemoglobin $\geq 9.0 \text{ g/dL}$
- v) Creatinine Serum creatinine $\leq 1.5 \times$ upper limit of normal (ULN) or creatinine clearance $> 40 \text{ mL/minute}$ (using Cockcroft/Gault formula)
- vi) AST $\leq 3 \times$ ULN
- vii) ALT $\leq 3 \times$ ULN

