viii) Total Bilirubin $\leq 1.5 \times \text{ULN}$ (except subjects with Gilbert Syndrome who must have total bilirubin $< 3.0 \text{ mg/dL}$)

- Subject Re-enrollment: This study permits the re-enrollment of a subject that has discontinued the study as a screen failure (ie, subject has not been randomized / has not been treated). If re-enrolled, the subject must be re-consented.

3. Age and Reproductive Status

- Men and women, at least 18 years of age
- Women of childbearing potential (WOCBP) must have a negative serum or urine pregnancy test (minimum sensitivity 25 IU/L or equivalent units of HCG) within 24 hours prior to the start of study drug.
- Women must not be breastfeeding
- WOCBP must agree to follow instructions for method(s) of contraception for the duration of treatment with study drug (s) plus 5 half-lives of study drug plus 30 days (duration of ovulatory cycle). The half-life of nivolumab and ipilimumab is up to 25 days and 18 days, respectively. WOCBP should therefore use an adequate method to avoid pregnancy for a total of 23 weeks post-treatment completion (Appendix 3).
- Men who are sexually active with WOCBP must agree to follow instructions for method(s) of contraception for the duration of treatment with study drug (s) plus 5 half-lives of the study drug (s) plus 90 days (duration of sperm turnover). The half-life of nivolumab and ipilimumab is up to 25 days and 18 days, respectively. Men should therefore use an adequate method of contraception for a total of 31 weeks post-treatment completion (Appendix 3).
- Azoospermic males and WOCBP who are continuously not heterosexually active are exempt from contraceptive requirements. However, they must still undergo pregnancy testing as described in this section.

Investigators shall counsel WOCBP and male subjects who are sexually active with WOCBP on the importance of pregnancy prevention and the implications of an unexpected pregnancy. Investigators shall advise WOCBP and male subjects who are sexually active with WOCBP on the use of highly effective methods of contraception. Highly effective methods of contraception have a failure rate of $< 1\%$ when used consistently and correctly. (Refer to Appendix 3.)

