4 INVESTIGATIONAL PLAN

4.1 Study Design and Duration

The study design schematic is presented in Figure 3.1-1.

Figure 4.1-1: Study Design Schematic

The subjects will be treated in both arms until disease progression, unacceptable toxicity, or subject withdrawal of consent.

This study will consist of three phases: screening, treatment, and follow-up. For a complete list of study required procedures, please refer to [Section 5](#).

Screening Phase:

- Begins by establishing the subject's initial eligibility and signing of the informed consent form (ICF).
- Subject is assessed for complete study eligibility within the required timeframe found in Table 7.1-1.
- A pregnancy test for WOCBP should be documented within 24 hours prior to the start of the first dose of study medication.
- All subjects must have at least 2 distinct lesions as documented by a complete physical examination or imaging studies within 4 weeks prior to randomization. Imaging studies must include a CT scan of the involved disease sites and all known sites of resected disease and brain magnetic resonance (MRI) or CT (brain CT allowable if MRI is contraindicated or if there is no known history of resected brain lesions).

Treatment Phase:

- Following confirmation of the subject's eligibility, the randomization call to the Moffitt Cancer Center Biostatistics Core can be made. The subject is randomly assigned to the Arm A (nivolumab + ipilimumab) or Arm B (nivolumab + ipilimumab + SBRT).
- Within 2 weeks from randomization the subject must receive the first dose of study medication (Day 1 of Week 1)
- On-study laboratory assessments should be drawn within 72 hours prior to dosing
- Adverse event assessments for grade ≥ 2 toxicities should be documented at each clinic visit and WOCBP must have a pregnancy test every four weeks +/- 1 week.
- Treated subjects will be evaluated for recurrence every 12 weeks +/- 7 days
- Patient Reported Outcome (PRO) instruments must be completed after randomization, prior to the dose of study therapy.

Follow-up Phase:

- Begins after 1 year of treatment or when the decision is made to discontinue a subject from study therapy.
- Patient may continue on the study drug under the treatment protocol indefinitely during the follow-up phase.
- After completion of the first two follow-up visits, subjects will be followed every 3 months for survival.

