 - If a subject has a baseline AST, ALT, or total bilirubin that is within normal limits, delay dosing for drug-related Grade ≥ 2 toxicity
 - If a subject has baseline AST, ALT, or total bilirubin within the Grade 1 toxicity range, delay dosing for drug-related Grade ≥ 3 toxicity
- Any adverse event, laboratory abnormality, or intercurrent illness which, in the judgment of the investigator, warrants delaying the dose of study medication.

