Review of concomitant medications	x	x	x	x	x	x	
Pregnancy Test	x			x		x	Every 4 weeks \pm 1 week. Serum or Urine.
Laboratory Tests	x		x	x	x	x	Within 72 hrs prior to dosing/SBRT to include CBC w/differential, LFT's, BUN or serum urea level, creatinine, Ca, Mg, Na, K, Cl, LDH, Glucose, amylase, lipase, TSH (with reflexive Free T4/T3)
Exploratory Biomarker Assessments							
Plasma	x	x	x		x		Prior to dosing/SBRT
Peripheral Blood Mononuclear Cells (PBMCs)	x	x	x		x		Prior to dosing/SBRT
Efficacy Assessments							
Surveillance Assessments	Every 12 weeks (\pm 7 days) from first dose of study treatment through 12 months (until distant recurrence)						Clinical exam and/or CT scan of the involved disease sites and all known sites of resected disease and brain MRI (brain CT allowable if MRI is contraindicated or if there is no known history of resected brain lesions). Use same imaging method as was used at screening/baseline.
Study Drug							
Randomize	x						
Study Treatment	x	RT	x	x	x	x	First dose to be administered within 14 days of randomization. See Section 5.5.
Outcome Research							
EORTC-QLQ-C30	x				x		Prior to dosing. D1W1 should be completed after randomization but prior to dosing.
EQ5D (optional)	x				x		
WPAI:GH (optional)	x				x		
Health Care Resource Utilization (optional)	x				x		

Table 7.1-3: On-Treatment Assessments Week 11 - Week 21

Procedure	Wk11	Wk13	Wk15	Wk17	Wk19	Wk21	Notes
Safety Assessments							
Targeted Physical Examination	x	x	x	x	x	x	
Vital Signs	x	x	x	x	x	x	Including BP, HR, temperature
Oxygen saturation	x	x	x	x	x	x	By pulse oximetry prior to dosing
Weight and performance status	x	x	x	x	x	x	Within 72 hours of dosing
Adverse Events Assessment	Continuously						See Section 6.8. and Section 8
Review of concomitant medications	x	x	x	x	x	x	
Laboratory Tests	x	x	x	x	x	x	Within 72 hrs prior to dosing to include CBC w/differential, LFT's, BUN or serum urea level, creatinine, Ca, Mg, Na, K, Cl, LDH, Glucose, amylase, lipase, TSH (with reflexive Free T4 and T3)
Pregnancy Test		x		x		x	Every 4 weeks ± 1 week. Serum or Urine.
Exploratory Biomarker							
Plasma		x					Prior to dosing
Peripheral Blood Mononuclear Cells (PBMCs)		x					Prior to dosing
Efficacy Assessments							

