Work Productivity and Activity Impairment: General Health (WPAI:GH) is a 6-item questionnaire yielding four different types of scores. The WPAI:GH was created as a patient-reported quantitative assessment of the amount of absenteeism (work time missed), presenteeism (impairment at work), work productivity (overall work impairment/absenteeism plus presenteeism) and daily activity impairment attributable to general health. WPAI:GH outcomes are expressed as impairment percentages, with higher numbers indicating greater impairment and less productivity, ie, worse outcomes. The recall period in all WPAI:GH validation studies is 7 days. The general literature on recall burden suggests that a longer recall period would not be suitable for the type of information being elicited in the WPAI:GH. In theory, a shorter recall period would improve accuracy of WPAI:GH responses, but this has not been tested. Assessment of work productivity will be conducted at each site (or remotely) with the appropriately translated and validated version of the WPAI:GH. All PRO instruments will be administered during on-study, and follow-up phases as outlined in Tables of Section 5.1, respectively, to all randomized subjects. Healthcare resource utilization data (eg, hospitalizations, non-protocol specified medical visits, diagnostics, etc) will be collected for all randomized subjects. The resource utilization capture is specific to hospital admission utilization data and non-protocol specified visits related to study therapy. Resource utilization questions will be asked as outlined in Table of Section 5.1 during screening, on-study, and follow-up phases, respectively.

An **Adverse Event (AE)** is defined as any new untoward medical occurrence or worsening of a preexisting medical condition in a clinical investigation subject administered study drug and that does not necessarily have a causal relationship with this treatment. An AE can therefore be any unfavorable and unintended sign (such as an abnormal laboratory finding), symptom, or disease temporally associated with the use of study drug, whether or not considered related to the study drug.

The causal relationship to study drug is determined by a physician and should be used to assess all adverse events (AE). The causal relationship can be one of the following:

Related: There is a reasonable causal relationship between study drug administration and the AE.

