9.2.2 Secondary Endpoint(s)

The first secondary endpoint is PFS. PFS will be programmatically determined based on the disease progression date provided by the investigator and is defined as the time between the date of randomization and the date of first progression (local, regional or distant metastasis) or death (whatever the cause), whichever occurs first. (Note: a subject who dies without reported progression will be considered to have progressed on the date of death.) For subjects who remain alive and whose disease has not progressed, PFS will be censored on the date of last evaluable disease assessment.

The second secondary endpoint (OS) is defined as the time between the date of randomization and the date of death. For subjects without documentation of death, OS will be censored on the last

date the subject was known to be alive. OS will be followed continuously while subjects are on the study drug and every 3 months via in-person or phone contact after subjects discontinue the study drug.

To third secondary endpoint to compare the local control of irradiated tumor provided by SBRT in combination with nivolumab versus nivolumab and ipilimumab will be assessed by the local control rate of the irradiated lesion.

The fourth secondary endpoint (to assess the safety and tolerability of nivolumab, SBRT and ipilimumab) will be measured by the incidence of adverse events, serious adverse events, deaths, and laboratory abnormalities.

The fifth secondary endpoint (to evaluate PD-L1 expression as a predictive biomarker) will be measured by the endpoint RFS based on PD-L1 expression level.

The sixth secondary objective (to evaluate HRQoL) will be measured by mean changes from baseline in the EORTC-QLQ-C30 global health status/QoL composite scale and by mean changes from baseline in the remaining EORTC QLQ-C30 scales in all randomized subjects.

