9.3.3 Safety Analyses

Safety analyses will be performed in all treated subjects. Descriptive statistics of safety will be presented using NCI CTCAE version 4.0 by treatment group. All on-study AEs, treatment-related AEs, SAEs, and treatment-related SAEs will be tabulated using worst grade per NCI CTCAE v 4.0 criteria by system organ class and preferred term. On-study lab parameters including hematology, chemistry, liver function, and renal function will be summarized using worst grade NCI CTCAE v 4.0 criteria.

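### Laboratory data are summarized by worst on-study grade with no baseline reference, so abnormalities present before treatment are counted

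*Combined protocol and SAP*

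**What the plan says.** Section 9.2.2 defines the fourth secondary endpoint, safety and tolerability, as one that "will be measured by the incidence of adverse events, serious adverse events, deaths, and laboratory abnormalities". Section 9.3.3 gives the rule for laboratory values, applied to all treated subjects: "On-study lab parameters including hematology, chemistry, liver function, and renal function will be summarized using worst grade NCI CTCAE v 4.0 criteria". It contains no shift table, no treatment-emergent rule and no comparison with a pre-dose value.

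The Synopsis (Analyses) adds that hematologic and non-hematologic toxicity will be graded by CTCAE and compared between the arms with Pearson's chi-square test. It does not say whether raw laboratory grades enter that test.

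On timing, Section 7.3 labels as baseline the samples taken within 14 days before randomization. Section 4.1 says: "On-study laboratory assessments should be drawn within 72 hours prior to dosing". Table 7.1-2 (Section 7.1), the on-treatment schedule, marks a laboratory draw at Week 1 with the note "Within 72 hrs prior to dosing/SBRT to include CBC w/differential".

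On values at entry, Section 3.1 ("Screening laboratory values must meet the following criteria") admits AST and ALT up to 3 x ULN, hemoglobin from 9.0 g/dL and bilirubin up to 1.5 x ULN, with a wider bilirubin limit of below 3.0 mg/dL in Gilbert syndrome. Section 5.5.5 has its own dose-delay rule for such patients: "If a subject has baseline AST, ALT, or total bilirubin within the Grade 1 toxicity range". Section 5.5.6 likewise refers to a grade shift from baseline in these tests.

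**The concern.** Incidence in a safety endpoint is normally read as what arose or worsened under treatment. The protocol's own definition of an adverse event takes that view: "any new untoward medical occurrence or worsening of a preexisting medical condition". The dosing rules do the same for liver tests. The laboratory summary does not.

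Pre-treatment abnormalities enter it by two routes. The Week 1 sample precedes any study drug but sits among the on-study samples. And an abnormality present at entry that simply persists is shown at its grade, with nothing to separate it from one that began on treatment.

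At stake is how the laboratory rates in each arm are read. They would look like treatment effects when part of them is the patients' condition at entry.

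**Working it through.** The plan states no figure for the laboratory summary, so there is nothing to reproduce. The check has two parts.

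**1. Does the text count pre-treatment values?**
- Sections 4.1 and 7.3 use the on-study label for samples drawn around dosing, and Table 7.1-2 puts the Week 1 pre-dose draw in the on-treatment schedule. Section 9.3.3 takes the worst grade of on-study values. Followed literally, a value taken before any treatment can be a patient's worst grade.
- Section 5.5.5 shows that graded liver-test abnormalities at baseline are expected. For the other tests the documents do not reproduce the CTCAE cut-offs, so I do not claim a grade for them.
- Section 3.1 limits blood counts, creatinine, AST, ALT and bilirubin. It sets no limit for amylase, lipase, electrolytes or glucose, which Table 7.1-2 also measures.
- The first dose may follow randomization by up to 2 weeks (Section 5.5.1), so the screening sample can be up to 14 + 14 = 28 days old at first dose. The Week 1 draw is the natural baseline.

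**2. How large could the effect be?** The documents give no baseline abnormality rate, so the following is an illustration.

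Inputs: 24 patients per arm (Section 9.1.1, full enrolment). Assumed: k = 2 to 5 patients per arm abnormal before dosing, all persisting on study; a rate r of new or worsened abnormality of 20% in one arm and 40% in the other, applying to all patients whatever their baseline.

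Formulas:
- any-grade rate shown = k/24 + (1 - k/24) x r
- incident rate (new or worsened) = r
- overstatement = shown - r = (k/24) x (1 - r)

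| k per arm | Shown | Incident | Overstatement (points) | Difference shown | Incident difference |
|---|---|---|---|---|---|
| 2 | 26.7% vs 45.0% | 20% vs 40% | 6.7 and 5.0 | 18.3 | 20 |
| 5 | 36.7% vs 52.5% | 20% vs 40% | 16.7 and 12.5 | 15.8 | 20 |

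For k = 5 in the 20% arm: 5/24 + (19/24) x 0.20 = 0.208 + 0.158 = 0.367, and 0.367 - 0.20 = 0.167. The ratio of shown rates is 45.0/26.7 = 1.69 at k = 2 and 52.5/36.7 = 1.43 at k = 5, against an incident ratio of 2.0.

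Upper bound: if no patient who is abnormal at baseline ever worsens, the incident rate is (1 - k/24) x r and the overstatement is k/24 in each arm, which is 8.3 points at k = 2 and 20.8 at k = 5. In that limiting case only, the difference between arms is unchanged (18.3 points at k = 2, 15.8 at k = 5).

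Chance imbalance: with k = 2 in the 20% arm and k = 5 in the 40% arm, the shown difference is 52.5 - 26.7 = 25.8 points. With the counts reversed it is 45.0 - 36.7 = 8.3 points. The incident difference is 20 in both, so imbalance can push the comparison either way.

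**The case against.** The strongest reply is that a worst on-study grade table is accurate for what it says it shows, that Section 9.3.3 does not call it new onset, and that the cases that matter are caught elsewhere. Section 8.3 sends to the adverse event record any laboratory result that is clinically significant, meets the SAE definition, causes a dose to be omitted or stopped, or needs corrective therapy. Adverse events must be new or worsening. Dosing decisions already use baseline for AST, ALT and bilirubin. Randomization balances baseline abnormality on average.

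Most of this stands, and it limits the importance of the point. It does not remove it. Section 9.2.2 does call for incidence, and no other section says how laboratory incidence is to be derived. A low-grade change that meets none of the Section 8.3 conditions may be visible only in this table. Balance between arms does not correct the level within each arm.

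Three stronger readings are tempting, and the documents do not support them:
- A reader might infer that the Week 1 draw is left unclassified. The text groups it with the on-study samples and calls the screening samples baseline. The problem is where it is placed.
- A reader might infer that Section 9.3.3 is the only rule touching laboratory data, so that the effect stops at a descriptive table. The Synopsis also plans a chi-square comparison of hematologic and non-hematologic toxicity. That test is affected only if it uses raw laboratory grades, which the plan does not state.
- A reader might infer that the overstatement is k/24 in both arms and cancels in the difference. That needs equal k and no worsening among patients abnormal at baseline. Once worsening counts as incident, the shown difference shrinks as well.

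**Conclusion.** The point holds as a cheap improvement. The laboratory rule has no baseline reference, so abnormalities present before treatment are counted and mainly low-grade rates are overstated in each arm. The size cannot be derived from the documents. Under the assumed values it is about 5 to 17 points per arm, with a shown difference of 15.8 to 18.3 points instead of 20, and an upper bound of 8.3 to 20.8 points per arm. These figures rest on the assumed k and r, on every baseline abnormality persisting, and on equal k in the two arms.

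A reader might go further and infer that the safety comparison for SBRT is systematically biased. The documents do not support that. Nothing suggests that baseline abnormality differs by arm other than by chance. The adverse event tables, the primary response endpoint and the interim review of unanticipated Grade 3 or higher toxicity are essentially unaffected.

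**What to change.** In Section 9.3.3:
- define baseline for the laboratory analysis as the last value before the first dose, including the Week 1 pre-dose draw;
- restrict worst grade to values drawn after the first dose;
- count an abnormality as incident only if its grade is at least one higher than baseline;
- add tables of baseline grade by worst post-dose grade, by arm, with worsening to Grade 3-4 shown separately;
- apply the same rule to any laboratory-based toxicity in the chi-square comparison planned in the Synopsis.

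The definition is for analysis only, so the dosing rules in Sections 5.5.5 and 5.5.6 need not change. The cost is a few sentences and one added table. No new samples are needed, because the screening, Week 1 and later pre-dose draws are already scheduled. One thing must be confirmed: Section 7.3 warns that some assessments may not be captured in the eCRF, so the sponsor should check that baseline laboratory values are entered.

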9.3.4 Outcomes Research Analyses

EORTC QLQ C-30

The analysis of EORTC QLQ C-30 will be performed in all randomized who have an assessment at baseline and at least one follow-up assessment.

All scales and single items are scored on a categorical scales and linearly transformed to 0-to-100 scales with higher scores for a functional scale representing higher levels of functioning, higher scores for the global health status/quality of life representing higher levels of global health status/quality of life and higher scores for a symptom scale representing higher level of symptoms.

EORTC QLQ C-30 global health status/QoL composite scale data and the remaining EORTC QLQ C-30 scale data will be summarized by timepoint using descriptive statistics for each treatment arm. Exploratory analyses may be performed to examine differences between the 2 arms.

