1.4.10 Rationale for Quality of Life Evaluation

Available chemotherapy to treat patients with metastatic Merkel cell carcinoma has been associated with substantial toxicities and unclear clinical benefit. Evaluating quality of life (QoL) in oncology clinical studies is becoming increasingly important to understand the impact of benefit/risk from the patient perspective, and for quality of life adjustments for survival data used in economic models supporting access of new drugs. However, QoL data from investigational trials in this population are just emerging.

The EORTC QLQ C-30 will be used to assess changes from baseline of patients' QoL during and after treatment in the different arms of the study. The EQ-5D will be used to assess general health status and the data will be used to calculate utilities for use in economic models. The WPAI:GH questionnaire for measure of work and activity impairment exhibits strong validity and reliability, plus the ability to evaluate the results on impairment in financial terms. Employers are increasingly concerned about the burden of illness in their workforce and the associated financial impact. Additionally, some payers of healthcare and prescription drugs may want assurance that all cost implications have been considered. The costs of lost productivity, in addition to standard direct healthcare costs are increasingly required to meet requirements from health authorities for a broader societal perspective. The cost of lost productivity as measured by the WPAI:GH will as a result be included as a key cost component of the cost-effectiveness model of nivolumab.

With the emergence of patients that experience long-term survival with immunotherapies, payers, physicians and patients are beginning to question not only about the duration of survival (OS) but also the quality of survival after treatment discontinuation. Therefore, the EQ-5D-VAS will be utilized to assess the quality of survival during the follow-up and survival phase of the trial.

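### QLQ-C30 change is defined for all randomized subjects but summarized visit by visit over whoever returned a form, so late means probably lean towards patients doing better, by an unknown amount

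*Combined protocol and SAP*

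**What the plan says.** Quality of life by QLQ-C30 is a listed secondary objective (Section 1.3.2). Section 9.2.2 takes mean change from baseline as its measure, in the global scale and in the "remaining EORTC QLQ-C30 scales in all randomized subjects".

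Section 9.3.4 is narrower. The analysis will be "performed in all randomized who have an assessment at baseline and at least one follow-up assessment", and scale data will be "summarized by timepoint using descriptive statistics for each treatment arm". It does not mention change from baseline, missing forms, completion rates, deaths or a longitudinal model. On comparing arms it says only: "Exploratory analyses may be performed to examine differences between the 2 arms".

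Collection is intended to be broad. Section 7.6 states: "All PRO instruments will be administered during on-study, and follow-up phases as outlined in Tables of Section 5.1, respectively, to all randomized subjects". The schedule itself is in Section 7.1:

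- **On treatment (Tables 7.1-2 to 7.1-6):** QLQ-C30 at week 1 before dosing, then at weeks 7, 13, 19, 25, 31, 37, 43 and 49, all at dosing visits.
- **After treatment (Table 7.1-7):** QLQ-C30 at follow-up visits 1 and 2 only. These fall 30 days after the last dose and 84 days after that. Survival visits have no QLQ-C30.

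Treatment runs to progression, intolerable toxicity or withdrawal (Section 4.1), although Section 5.5.9 lets some patients continue past progression.

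**The concern.** A by-visit mean uses a different group of patients at each visit. If patients whose quality of life is falling leave the schedule sooner, the mean among those remaining rises even when nobody improves. Because on-treatment forms follow dosing, and dosing normally stops at progression or toxicity, such a link is plausible here. A patient with no form after baseline leaves the analysis altogether, although Section 9.2.2 counts that patient.

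Section 1.4.10 says the instrument is there to assess change from baseline "during and after treatment in the different arms of the study". A table of means by arm and visit will be read that way, and the week-49 row could show stable or improved quality of life when the randomized group as a whole declined. If time on treatment differed between arms, the selection could differ as well.

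**Working it through.** **There is no HRQoL figure in the plan to reproduce.** The sample size is set for response rate: the Simon design in Section 9.1.1 (2 of 16, then 6 of 24) recomputes exactly, with type I error 0.098 and power 0.901 per arm. The documents give no standard deviation, completion rate or dropout rate for QLQ-C30. The bias can therefore only be illustrated.

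**Inputs from the documents.** About 50 patients randomized 1:1 (Synopsis), so about 25 per arm. Forms at weeks 7 to 49 as listed above. The last QLQ-C30 form falls 30 + 84 = 114 days after the last dose.

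**Assumptions, not in the documents.** Exponential time on treatment with median 3, 6 or 12 months. No forms counted after treatment stops. True mean change 0 in all randomized patients. SD of change 20 points. Correlation r between change and time on treatment, on a normal-score scale.

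**Step 1: who is left.** The fraction still on the dosing schedule at week w is P = 0.5^((w − 1)/M), with M the median in weeks (months × 52.18/12 = 13.04, 26.09 or 52.18).

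| Median | Week 7 | Week 25 | Week 49 |
|---|---|---|---|
| 3 months | 0.73 (18 of 25) | 0.28 (7) | 0.08 (2) |
| 6 months | 0.85 (21) | 0.53 (13) | 0.28 (7) |
| 12 months | 0.92 (23) | 0.73 (18) | 0.53 (13) |

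**Step 2: bias in the mean of those left.** Bias = 20 × r × φ(z)/P, where z is the normal quantile exceeded with probability P. At week 49:

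| Median | φ(z)/P | r = 0 | r = 0.2 | r = 0.5 |
|---|---|---|---|---|
| 3 months | 1.87 | 0 | 20 × 0.2 × 1.87 = +7.5 | +18.7 |
| 6 months | 1.20 | 0 | +4.8 | +12.0 |
| 12 months | 0.75 | 0 | +3.0 | +7.5 |

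The range is therefore 0 when leaving is unrelated to quality of life, and about +3 to +19 points when r is 0.2 to 0.5. The signs apply to the global and functional scales. On symptom scales, where Section 9.3.4 scores high as worse, the same selection pulls the mean down.

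**Step 3: does a mixed model help at this sample size?** Simulations with 25 per arm, assumed variances and about 30–44% retained gave these errors at week 49:

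| Dropout depends on | By-visit mean of available forms | Random-slope mixed model |
|---|---|---|
| Last observed score | +7 to +13 | about −0.5 |
| Current, unseen score | +10 to +16 | +3 to +7 |

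The model had the lower root mean squared error in every case. Taken with Step 2, +5 to +15 points is a fair summary of the middle of the range when dropout is related to quality of life.

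**The case against.** **No between-arm HRQoL claim is planned.** The objectives compare PFS and OS but only evaluate HRQoL, arm comparisons are optional and exploratory, and the winner is chosen on response. This stands. A reader might infer that an observed arm difference would be an artefact, or that a trial conclusion is at risk. The documents support neither: no such difference is claimed, and nothing shows that time on treatment will differ by arm.

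**The population gap is small.** A change score needs a baseline and a later form, and Section 9.3.4 can be read as the evaluable part of the randomized set. This stands for the baseline form. The condition that can depend on outcome is the later form, and the two sections should still agree.

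**Selective dropout is inferred.** This stands. A reader might say outright that the missing forms belong to patients getting worse. The documents contain no attrition data, all randomized subjects are to be asked, two forms follow the end of treatment, and some patients may be treated past progression. These features soften the effect, and Step 1 leaves them out. They do not settle the matter: the follow-up visits are timed from the last dose, Section 9.3.4 does not say how they enter a by-timepoint table, and QLQ-C30 collection then stops.

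**Attrition will be visible.** The Synopsis has continuous variables described with the number of patients, so the count at each visit is already planned. This stands in part. A count shows that patients are missing, but not how many forms were expected or why they are absent.

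**A mixed model is over-ambitious for 25 per arm.** Precision is poor: in runs with 25 patients the week-49 estimate had an SD of roughly 6 to 8 points. Near-zero bias also appears only when dropout is simulated as missing at random, so it would be wrong to promise that the model removes the problem. Nevertheless, Step 3 shows that it does better than by-visit means at this size. A model that ignores death also projects scores beyond it, and the fix has to deal with that.

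**Conclusion.** The concern holds in a limited form. Sections 9.2.2 and 9.3.4 name different populations; that is plain from the text and needs no assumption. That later by-visit means lean towards patients doing better is likely, because the forms follow treatment and treatment normally ends at progression or toxicity, but it is not certain. The size cannot be found from the documents. The illustrative figures (0 if dropout is unrelated to quality of life, roughly +5 to +15 points at week 49 if it is related) rest on the assumed time on treatment, SD, correlation and dropout mechanism. They ignore or soften the role of the two follow-up forms. The effect is confined to a descriptive secondary endpoint and does not touch the response analysis. It is worth correcting because the correction is cheap, not because it threatens the trial.

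**What to change.** - **Population.** Name the same HRQoL population in Sections 9.2.2 and 9.3.4, and say in 9.3.4 that change from baseline is the quantity reported.
- **Model.** Add a likelihood-based mixed model for repeated measures on all available QLQ-C30 forms from randomized subjects. Terms: arm, time, arm-by-time and prior immunotherapy, with baseline as a response. Use a covariance or random-slope structure simple enough for about 25 per arm. Report mean change by visit and arm with 95% CI, as estimation and not as a test.
- **Follow-up forms.** Enter follow-up visits 1 and 2 by actual time since randomization.
- **Deaths.** State that estimates refer to patients while alive, or say how deaths are otherwise handled.
- **Sensitivity.** Add one analysis for dropout that is not at random, for example a pattern-mixture analysis.
- **Table.** Keep the descriptive table, with completed over expected forms by visit and arm.

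The cost is a little more analysis on data already scheduled for collection. Late estimates will be imprecise. The missing-at-random assumption reduces the bias but does not remove it if patients leave because of worsening that no form recorded. If the model is declined, the population wording and a rule for missing forms and deaths should still be corrected.
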